### 2.3 Standard Dose versus Low Dose Rituximab in ITP

Barriers to the use of adjuvant rituximab include cost and side effects. A standard course of rituximab (375 mg/m^2 weekly x 4) costs ~\$14,000. Complications of standard dosing include mild infusion reactions, and less commonly serum sickness or skin rash. Rare serious complications include (1 each) bronchospasm, anaphylaxis (non-fatal), transient cardiogenic shock, CMV reactivation, HZV myelitis, and fatal pneumonia among 306 patients with ITP (Arnold 2007) and 73 with TTP (Elliot 2009). Hepatitis B or C reactivation and progressive multifocal leukoencephalopathy are potential risks, but the incidence appears to be very low in autoimmune disorders (Stasi 2010).

The optimal dose for TTP is unknown and the current standard dose is based on regimens used to treat B cell lymphoma. In TTP and other autoimmune diseases the total B cell mass is much less than in patients with lymphoma and therefore a reduced dosage of rituximab might be sufficient.

For example, in a study of 11 patients with various autoimmune cytopenias, sustained complete responses to low dose rituximab (100 mg per week for 4 weeks) occurred in 4 of 7 patients with ITP and 1 patient with autoimmune pancytopenia. A partial response was observed in a patient with autoimmune hemolytic anemia, whereas no effect was observed in 1 patient each with pure red cell aplasia and autoimmune neutropenia (Provan 2007).

Several studies of ITP also suggest that low dose rituximab may be effective. In 48 patients with immune thrombocytopenia (ITP), low dose rituximab (100 mg per week for 4 weeks) induced overall and complete responses in 60.5 % and 39.5% of patients respectively. A review of 19 studies using full dose rituximab in ITP calculated overall and complete response rates of 62% and 46% (Arnold 2007), which is comparable to the results reported for low dose rituximab (Stasi 2010). In responders to low dose rituximab the median time to response was 35 days. 16 of 29 responders relapsed and 14 of them needed further treatment. The 12-month and 24-month cumulative relapse-free survival was 61% and 45%, respectively (Zafa 2010). A direct comparison of low-dose and standard-dose rituximab will be required to determine whether the low dose regimen is equivalent with respect to time to response and relapse rate.

## **2.4. Proposed Study of Low-Dose Adjuvant Rituximab for TTP**

The substitution of low dose for standard dose rituximab would reduce the drug cost 7-fold to approximately \$2,000 for a 4 week course, which approximates the cost of one plasma exchange procedure. Low dose rituximab (100 mg) may also have a decreased risk of complications. Two studies of low dose rituximab for ITP reported mainly mild infusional reactions. The rate of serious complications is probably low but not known precisely: one of 59 patients with ITP treated with low dose rituximab developed interstitial pneumonia that responded to steroids (Provan 2007, Zaja 2010).

Based on the currently available data we propose a pilot study to determine whether adjuvant low dose rituximab, in addition to standard therapy with plasma exchange and corticosteroids, can shorten the time to treatment response and reduce the risk of exacerbation for patients with TTP caused by ADAMTS 13 deficiency.

We will use a novel assay to evaluate the utility of ADAMTS 13 as a biomarker to assess the response to therapy and predict the risk of relapse. If successful this therapy would not only improve patient outcomes but also would be cost saving compared to standard dose, salvage rituximab, which is the current standard of care.

## **3. STUDY POPULATION**

### **3.1 Inclusion criteria**

- 1) Age  $\geq$ 18 years
- 2) Diagnosis of suspected TTP
  - a. Platelet count of  $<80,000/\mu\text{L}$  for newly diagnosed patients and  $<120,000/\mu\text{L}$  for relapsed patients
  - b. Microangiopathic hemolytic anemia (MHA) with RBC fragmentation
  - c. LDH  $>1 \times \text{ULN}$
- 3) Subjects who will receive treatment for TTP with plasma exchange
- 4) Subjects who have not started the 5TH plasma exchange.
- 5) Plasma ADAMTS13 activity  $<10\%$

### **3.2 Exclusion criteria**

- 1) Treatment for TTP within the past 2 months
- 2) Severe active infection indicated by sepsis (requirement for pressors with or without positive blood cultures) or clinical evidence of enteric infection with *E. coli* O157:H7 or related organism.
- 3) Currently under treatment for cancer or with a current diagnosis of cancer (subjects with localized skin carcinoma will be accepted)
- 4) Microangiopathic hemolytic anemia due to a mechanical heart valve
- 5) Severe hypertension, as defined by systolic BP  $>180$  AND diastolic BP  $>120$ , or papilledema
- 6) Organ or stem cell transplant

- 7) Use of calcineurin inhibitors (e. g., sirolimus, tacrolimus, cyclosporin A) within 6 months prior to diagnosis
- 8) Disseminated intravascular coagulation, as defined by:
  - a. INR >2.0 (unrelated to anticoagulation, unresponsive to vitamin K) **or**
  - b. Fibrinogen <100 mg/dL
- 9) Pregnancy
- 10) Known congenital TTP.
- 11) Rituximab within the previous year.
- 12) HIV history or positive serology
- 13) History of hepatitis B or positive serology for HBsAg or Anti-HBc
- 14) Persistent or unexplained platelet count below 150,000/ $\mu$ L within 3 months of current TTP presentation
- 15) Hypersensitivities or allergies to murine and/or humanized antibodies
- 16) Current participation in trials of investigational therapies or devices, except that investigational central catheters are not exclusions

#### **4. STUDY ENROLLMENT**

##### **4.1 Recruitment and screening**

Subjects will be recruited through the Transfusion Medicine or Hematology Consult services at Washington University and up to 5 additional sites. A potentially eligible subject will be identified by his or her physician. Once a potentially eligible subject is identified, and after the treating staff has obtained permission from the subject to be contacted, a member of the study staff will contact the subject, describe the study, and obtain consent.

After signing the consent form the subject will be assigned a study ID number and study staff will determine if the subject is eligible based on his or her medical history and laboratory results. A subject is considered enrolled in the study after the informed consent document is signed by the subject and the subject meets all eligibility criteria. Within one day (Monday-Friday) after enrollment, the site should submit a copy of the Inclusion/Exclusion Criteria Checklist that has been signed by a site investigator to the Washington University Clinical Coordinating Center.

#### **5. STUDY INTERVENTION AND CONCOMITANT THERAPIES**

##### **5.1 Rituximab**

###### **5.1.1 Description**

The RITUXAN® (rituximab) antibody is a genetically engineered chimeric murine/human monoclonal antibody directed against the CD20 antigen found on the surface of normal and malignant B lymphocytes. The antibody is an IgG1 kappa immunoglobulin containing murine light- and heavy-chain variable region sequences and human constant region sequences. Rituximab is composed of two heavy chains of 451 amino acids and two light chains of 213 amino acids (based on cDNA analysis) and has an approximate molecular weight of 145 kD. Rituximab has a binding affinity for the CD20 antigen of approximately 8.0 nM.

The chimeric anti-CD20 antibody is produced by mammalian cell (Chinese Hamster Ovary) suspension culture in a nutrient medium containing the antibiotic gentamicin. Gentamicin is not detectable in the final product. The anti-CD20 antibody is purified by affinity and ion exchange chromatography. The purification process includes specific viral inactivation and removal procedures. Rituximab drug product is manufactured from bulk drug substance manufactured by Genentech, Inc. (US License No. 1048).

Rituximab is a sterile, clear, colorless, preservative-free liquid concentrate for intravenous (IV) administration. Rituximab is supplied at a concentration of 10 mg/mL in either 100 mg (10 mL) or 500 mg (50 mL) single-use vials. The product is formulated for IV administration in 9 mg/mL sodium chloride, 7.35 mg/mL sodium citrate dihydrate, 0.7 mg/mL polysorbate 80, and Water for Injection. The pH is adjusted to 6.5.

### **5.1.2 Administration**

Each study site will utilize its own supply of rituximab, and will store under conditions consistent with the drug's package insert. The prescribed dose of rituximab will be reconstituted in normal saline to a concentration no more than 4 mg/mL. Rituximab dose is fixed dose of 100 mg, given intravenously, repeated at one-week intervals for a total of four doses. Rituximab is to be administered only by slow intravenous infusion; it is not to be administered as an IV push or bolus. The infusion may be administered via a peripheral venous catheter; no central catheter is required. Treatment may be on an out-patient basis; in-patient hospitalization is not required. Each rituximab infusion bag will be labeled by the pharmacy as "Investigational Drug – ART Study". An Investigational Drug Accountability Log will be provided to each site by the sponsor-investigator and will be maintained by personnel at each study site. This Log will be updated by study personnel each time rituximab is dispensed by the pharmacy and a copy will be provided to the site research coordinator and the Washington University liaison. All expired or unused drug will be destroyed in accordance with local institutional practice.

Rituximab is to be infused every 7 days with a window of 5-9 days considered acceptable. If a dose is administered outside the 5-9 day window, then the schedule will be altered such that the next dose will be given 7 days later and any subsequent doses will be given at 7 day intervals.

The first rituximab infusion will be given as soon as possible after study eligibility is established but before the 5th plasma exchange.

The initial rituximab solution for infusion will be administered intravenously at an initial rate of 50 mg/hr. Subsequent rituximab infusion can be administered at an initial rate of 100 mg/hr.

### **5.1.3 Pre-medication**

Pre-medication with oral acetaminophen, diphenhydramine for prevention of reactions to rituximab is strongly recommended. If the patient has started or completed the taper of prednisone consider a single dose of 100 mg methyl prednisone before rituximab infusion.

### **5.1.4 Administration While on Plasma Exchange**

The rituximab infusion is to be given immediately after plasma exchange. The next plasma exchange is to be performed as late as possible in order to maximize exposure to rituximab. At least a 20-hour time interval between rituximab and plasma exchange is the goal. Plasma exchange is not to be performed sooner than 12 hours after the end of a rituximab infusion.

### **5.1.5 Administration After Plasma Exchange**

Subjects who are no longer receiving plasma exchange may continue to receive the remainder of the four weekly rituximab infusions on an outpatient basis. Each subject receiving rituximab as an outpatient will be contacted by study personnel by telephone the day after each infusion to assess medical status.

### **5.1.6 Interrupting Infusions**

Rituximab infusion will be interrupted for severe reactions. In most cases, the infusion can be resumed at a 50% reduction in rate (e.g. from 100 mg/hr to 50 mg/hr) when symptoms have completely resolved. Treatment of infusion related symptoms with diphenhydramine and acetaminophen is recommended. Additional treatment with bronchodilators or IV saline may be indicated. Most subjects who have experienced non-life-threatening infusion-related reactions have been able to complete the full course of rituximab therapy. Epinephrine, antihistamines and corticosteroids will be available for immediate use according to hospital procedures for an emergent situation such as hypersensitivity reaction to rituximab (e.g. anaphylaxis).

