##### Severe Infusion Reactions

Rituximab can cause severe, including fatal, infusion reactions. These severe reactions typically occurred during the first infusion with time to onset of 30 to 120 minutes. Monitor closely during infusion; discontinue with grade 3 or 4 infusion reactions. Signs and symptoms of

severe infusion reactions may include urticaria, hypotension, angioedema, hypoxia, or bronchospasm, and may require interruption of rituximab administration. The most severe manifestations and sequelae include pulmonary infiltrates, acute respiratory distress syndrome, myocardial infarction, ventricular fibrillation, cardiogenic shock, and anaphylactic and anaphylactoid events. In the reported cases, the following factors were more frequently associated with fatal outcomes: female gender, pulmonary infiltrates, and chronic lymphocytic leukemia or mantle cell lymphoma.

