### **Hypersensitivity reactions**

Rituximab has been associated with hypersensitivity reactions (non-IgE-mediated reactions), which may respond to adjustments in the infusion rate and in medical management. Hypotension, bronchospasm, and angioedema have occurred in association with rituximab infusion (see Severe Infusion Reactions). Therefore, subjects require close monitoring during first and all subsequent infusions. Premedication with diphenhydramine and acetaminophen is recommended.

Rituximab infusion will be interrupted for severe hypersensitivity reactions and can be resumed at a 50% reduction in rate (e. g., from 100 mg/hour to 50 mg/hour) when symptoms have completely resolved. Treatment of these symptoms with diphenhydramine and acetaminophen is recommended; additional treatment with bronchodilators or IV saline may be indicated. In most cases, patients who have experienced non-life-threatening hypersensitivity reactions have been able to complete the full course of therapy. Medications for the treatment of hypersensitivity reactions, e. g., epinephrine, antihistamines, and glucocorticoids, should be available for immediate use in the event of a reaction during administration.

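### Section 5.1.6 and the hypersensitivity text of 7.1.2 allow a half-rate restart after a resolved severe reaction, another paragraph of 7.1.2 says to discontinue at grade 3 or 4, and nothing says which governs

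*Combined protocol and SAP*

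**What the plan says.** Three places in the combined protocol and SAP tell the site what to do when a rituximab infusion causes a severe reaction.

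- **5.1.6 Interrupting Infusions:** "Rituximab infusion will be interrupted for severe reactions. In most cases, the infusion can be resumed at a 50% reduction in rate". The condition is complete resolution of symptoms. No CTC grade is named. The section adds that most people with reactions that were not life-threatening finished their course.
- **7.1.2, Hypersensitivity reactions:** "Rituximab infusion will be interrupted for severe hypersensitivity reactions and can be resumed at a 50% reduction in rate", on the same condition. It adds that in most cases "patients who have experienced non-life-threatening hypersensitivity reactions have been able to complete the full course of therapy", and on monitoring it says "Therefore, subjects require close monitoring during first and all subsequent infusions".
- **7.1.2, Severe Infusion Reactions:** "Monitor closely during infusion; discontinue with grade 3 or 4 infusion reactions". The next sentence is softer. It says that signs and symptoms of "severe infusion reactions may include urticaria, hypotension, angioedema, hypoxia, or bronchospasm, and may require interruption of rituximab administration". On timing it says "These severe reactions typically occurred during the first infusion with time to onset of 30 to 120 minutes".

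Section 7 adopts the CTC scale, on which grade 3 is severe and grade 4 is life-threatening or disabling. Section 7.1.2 introduces the paragraphs on reactions as information from the package insert. Section 8.1 lists three reasons for removal from rituximab: early salvage therapy, repeated exacerbation, and plasma exchange too soon after an infusion. None concerns an infusion reaction.

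**The concern.** A site treating a grade 3 bronchospasm or hypotension that has fully resolved can find two answers. Section 5.1.6, where infusion staff would look first, lets them restart at half rate. The Severe Infusion Reactions paragraph tells them to discontinue.

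What is at stake is re-exposure of a patient who has just had a serious reaction, and any event that follows. The same paragraph warns that such reactions can be fatal. Section 4.1 allows up to five sites besides Washington University, and 5.1.2 and 5.1.5 allow outpatient dosing, so practice could differ between sites. The reaction that triggered the decision is reported either way.

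**Working it through.** **Step 1. Do the texts cover the same event?** Section 5.1.6 and the hypersensitivity paragraph speak of severe reactions and give no grade. On the scale in section 7, severe is grade 3. This is an inference, since that scale is introduced for reporting adverse events. It is supported by the paragraph headed Severe Infusion Reactions, which itself attaches grades 3 and 4. The clinical signs overlap too: hypotension, bronchospasm and angioedema appear in both 7.1.2 paragraphs, and the hypersensitivity paragraph points the reader to the other one.

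**Step 2. Apply each text to a resolved reaction.**

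| Reaction | 5.1.6 | 7.1.2 Hypersensitivity | 7.1.2 Severe Infusion Reactions |
|---|---|---|---|
| Grade 3, resolved | restart at half rate permitted | restart at half rate permitted | discontinue |
| Grade 4 | wording on course completion points away from restart | same | discontinue |

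The conflict is sharpest at grade 3. A site that stops at grade 3 complies with all three texts, because the restart is permitted and not required. A site that restarts complies with two and departs from the third.

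**Step 3. Does anything else settle it?** No precedence is stated, and 8.1 is silent. On later weekly doses the text leans towards continuing:

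- Both resumption paragraphs say that most patients whose reactions were not life-threatening completed the course.
- The cardiovascular paragraph of 7.1.2 stops infusions for serious arrhythmias, and then requires cardiac monitoring at subsequent infusions after clinically significant ones.
- The mucocutaneous paragraph bars further infusions in so many words, which shows how the protocol writes a permanent stop when it means one.

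**Step 4. How much drug is involved?** The plan gives no figure to reproduce. Inputs from 5.1.2: 100 mg per dose, four doses (400 mg), initial rate 50 mg/hr for the first infusion and 100 mg/hr for later ones. Assumption: the initial rate stays constant, since no escalation schedule is given.

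Remaining dose = 100 − rate × (onset in minutes / 60). Restart time = remaining dose / (rate / 2).

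| Infusion | Onset | Remaining | Share of 400 mg | Restart time |
|---|---|---|---|---|
| First | 10 min | 100 − 8.3 = 91.7 mg | 22.9% | 91.7 / 25 = 3.7 h |
| First | 30 min | 100 − 25 = 75 mg | 18.75% | 75 / 25 = 3 h |
| First | 60 min | 100 − 50 = 50 mg | 12.5% | 50 / 25 = 2 h |
| First | 90 min | 100 − 75 = 25 mg | 6.25% | 25 / 25 = 1 h |
| First | 120 min | 0 mg | 0% | none |
| Later | 30 min | 100 − 50 = 50 mg | 12.5% | 50 / 50 = 1 h |

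The 30 to 120 minute range is described only as typical, so 30 minutes is not a minimum; the 10-minute row shows an earlier onset. The protocol gives that range for first infusions, and using 30 minutes for a later one is an assumption. At 120 minutes the first infusion is complete and no conflict arises.

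**The case against.** The best defence is that these are not two competing trial rules. The Severe Infusion Reactions paragraph sits under a heading about expectedness of adverse events, is introduced as package-insert content, and uses general imperatives. Section 5.1.6 is the dosing section and agrees with the hypersensitivity paragraph. Its wording is permissive and allows exceptions, which the grade 3 or 4 instruction could supply.

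Part of this stands. The likely origin is a label sentence that was never harmonised, and the link between severe and grade 3 is inferred. But setting 7.1.2 aside as background does not work. It contains trial directives, including the mucocutaneous bar, and the two conflicting paragraphs both sit inside it. Nor do the exceptions reconcile the texts: if every grade 3 or 4 reaction ended the infusion, resumption could not be the usual course after severe reactions.

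A reader might also infer more than the text supports:

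- *That sites must re-infuse after grade 3.* They need not; resumption is only permitted.
- *That discontinuing at grade 3 ends rituximab for good.* The word is not defined, and the surrounding text points to stopping that infusion.
- *That 75 mg is a ceiling.* It is not, since onset can be earlier than 30 minutes.
- *That the primary comparison is affected.* Nothing in the documents shows this.

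**Conclusion.** The protocol is internally inconsistent on a safety instruction. For a resolved grade 3 infusion reaction, a site that restarts under 5.1.6 does what the Severe Infusion Reactions paragraph rules out, and nothing in the document decides between them. This rests on reading severe as grade 3, which is the most natural reading but is not stated.

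The practical size is small. The drug in question is about 75 mg of 400 mg for a first infusion stopped at 30 minutes at a constant rate, varying with onset. The documents give no grade 3 or 4 reaction rate at this dose; section 2.4 describes mostly mild reactions, and 9.1 plans 20 patients, so few are likely to be affected. It deserves correction because it concerns patient safety and staff need one answer at the bedside.

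**What to change.** Put the same text in 5.1.6 and in the hypersensitivity paragraph of 7.1.2:

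> An infusion interrupted for a reaction below CTC grade 3 may be resumed at half rate when symptoms have completely resolved. A grade 3 or 4 infusion reaction ends that infusion. Later weekly doses may be given after a resolved grade 3 reaction, with premedication and close monitoring, but not after a grade 4 reaction.

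The rule on later doses follows the direction of the existing text (step 3). If the sponsor does intend resumption at grade 3, the alternative is to leave that permission in place and amend the Severe Infusion Reactions paragraph to stop at grade 4. That is a clinical choice for the sponsor.

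Either way the change is to wording only, with no added procedures. Under the proposed text, the cost is the unfinished part of the ended infusion (step 4) in the few patients affected. After a grade 4 reaction the remaining doses are lost as well. If it occurred at the first infusion, that is a further 3 × 100 = 300 mg.

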## **5.2 Plasma Exchange and Corticosteroids**

### **5.2.1 Initial Treatment with Plasma Exchange and Corticosteroids**

The target for plasma replacement is 1.5 plasma volumes. Fresh frozen plasma (FFP) is the preferred replacement fluid. Frozen plasma 24 (plasma frozen with 24 hours of draw) or cryoprecipitate-poor plasma (CPP) may be used if FFP is not available. Some clinicians may prefer to switch to CPP replacement and this is acceptable. Prophylaxis for reactions to plasma during plasma exchange is at the investigator's discretion.

Each subject will also be given 1 mg/kg of prednisone (or equivalent) (within a margin of 10%) per day. Subjects with medical contraindications for steroid therapy (e. g. history of psychosis, brittle or uncontrolled diabetes, peptic ulcer disease, poorly controlled hypertension, or severe osteoporosis) may have corticosteroids withheld. The following prophylaxis will be used for corticosteroids:

- Gastric protection is strongly encouraged, but the method is at the investigator's discretion.
- Thrush and pneumocystis prophylaxis will be at the investigator's discretion.

